**Storage and stability:**

Alvimopan capsules may be stored at controlled room temperature (77° F) with excursions between 59° and 86° F.

**Preparation:**

Alvimopan and placebo will be over-encapsulated by USCD pharmacy prior to administration.

**Route of administration for this study:**

Study drug (alvimopan or placebo) will be administered orally. If a gastric or nasogastric tube is present, it will be clamped for one hour after oral administration of the study drug.

**Side effects:**

The most common adverse events of alvimopan include the following:

- Hypokalemia (10%)
- Dyspepsia (2-7%)
- Anemia (5%)
- Urinary retention (3%)
- Back pain (3%)
- Myocardial infarction (rate unknown, higher rate than placebo in study with 12 month use of alvimopan)

**8.1.1 Return and Retention of Study Drug**

Remaining drug is to be destroyed, according to Moores Cancer Center Investigational Drug Services destruction policy.

**8.1.2 Subject Compliance**

Subject compliance of study drug will be maintained by directly-observed administration in the hospital.

**9.0 STATISTICAL CONSIDERATIONS**

---

**9.1 Study Design/Study Endpoints**

The proposed study is a double blind prospective, randomized controlled phase 2 trial.

Subjects will be assigned 1:1 to either placebo or alvimopan groups using a permuted block randomization of block size 4. The block and package in the R statistics software will be used to generate group assignments. The randomization file will be given to the investigational Pharmacy which will carry out the randomization. Patients who do not undergo CRS/HIPEC during surgery are considered screen failures after randomization. Their randomization IDs will not be discarded and will be passed to the next available subjects to keep the 1:1 ratio.

**9.2 Sample Size and Accrual**

Our sample size calculation is based on detecting a difference in distributions of times until GI-2 between groups. Assuming a similar hazard ratio between the Alvimopan 12 mg and placebo groups as Xu et. al. (HR = 1.59, which approximately corresponds to an improvement in the median primary endpoint (GI-2) from 9 days to 5.7 days), a log-rank test for a difference in distributions of times until GI-2 is met will have 80% power at the one sided 0.05 significance level with a total sample size of n = 122. (Note that this does not adjust for a reduction in power due to the interim analysis.) Accounting for a 5% drop-out rate, the total enrolled sample size is 128 participants.

Approximately 60-70 CRS/HIPEC procedures are performed at UCSD annually. Accrual of 128 participants could occur over 2-3 years. Annual target accrual will be 40 participants per year.

Accrual Targets			
Ethnic Category	Sex/Gender		
	Females	Males	Total
Hispanic or Latino	8	5	13
Not Hispanic or Latino	63	52	115
Ethnic Category: Total of all subjects	71	57	128
Racial Category			
American Indian or Alaskan Native	0	0	0
Asian	8	5	13
Black or African American	2	1	3
Native Hawaiian or other Pacific Islander	1	1	2
White	60	50	110
Racial Category: Total of all subjects	71	57	128

### 9.3 Protocol Deviations, Data Blind Review, and Unblinding

Classification of deviations from the protocol as minor or major, and decisions regarding exclusion of patients and/or patient data from the statistical analyses, will be decided on a case-by-case basis without knowledge of the treatment assigned and before the database lock (Data Blind Review). After database lock, the responsible statistician will request the treatment codes, the study will be unblinded, and the statistical analysis will be conducted.

### 9.4 Analysis Populations

Analysis populations are defined as follows:

- The Safety population will include all randomized patients who took at least one dose of the study medication, including screen failures after randomization and subjects withdrawn from the study.
- The modified Intent-to-Treat (mITT) population will include all randomized patients who took at least one dose of the study medication and who have at least one efficacy evaluation following baseline.
- The Per Protocol (PP) population will include all mITT patients who:
  - took assigned medication during the treatment period (who received at least 50% of the study drug), and
  - did not have any major protocol deviations.

The primary population for all efficacy analyses is the mITT population, without imputation for missing values. Sensitivity analyses will also be performed using the PP populations

for efficacy endpoints, and using the mITT population with multiple imputation. The safety population will be used for analyses of safety endpoints.

### **9.5 Analyses of the primary endpoint**

For our primary endpoint, we will use a log-rank test at 5% level to compare the distributions of times until recovery (GI-2) between groups.

### **9.6 Analyses of secondary endpoints**

Log-rank test will also be used to compare the time to return of bowel function outcome. A Cox proportional hazards model will also be considered for this endpoint, controlling for potential confounders such as age and gender. The proportion of patients with prolonged ileus will be compared between groups with a Pearson's chi square test. A logistic regression model will be used to assess the association between prolonged ileus and treatment, controlling for potential confounders. We will compare the time to discharge between groups with a two-sample t-test, and consider a linear regression to control for potential confounders, including opioid use (i.e. total morphine equivalents) +/- epidural placement, bowel resection, and other complications.

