The median length of stay after CRS/HIPEC is 10 days at our institution. A majority of the hospital stay is comprised of awaiting return of bowel function. The first flatus or bowel movement does not typically occur until postoperative day 4-5, and in 13% of patients it takes longer than 7 days. This is despite the fact that all patients undergo enhanced recovery pathways; including early mobilization, foley catheter removal as soon as feasible, and early advancement to liquid diet. Although attempts are made to minimize narcotic use after CRS/HIPEC - including use of epidural catheters and opioid-sparing medications (such as ketorolac and lidocaine patch) – all patients still require postoperative narcotics, which likely contributes to the prolonged ileus.

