### **2.2 Secondary Objectives**

1. To determine the proportion of prolonged ileus (> 7 days) in each group
2. To determine the time to return of bowel function components in each group: time to first flatus, time to first bowel movement, time to tolerance of solid food
3. To determine the time to hospital discharge order written in each group
4. To measure the adverse event rate in each group
5. To perform subgroup analyses on each group: 0 vs. 1 or greater anastomoses, 0 vs. 1 or greater visceral resection, high vs. low amount of postoperative narcotic use (above or below the median total postoperative morphine equivalent dose of narcotics), epidural vs. no epidural

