#### **6.1.1 Prolonged Ileus**

Participants without flatus or BM for more than seven days after surgery, are considered to have a prolonged ileus.

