### **9.7 Exploratory analyses**

For any prespecified subgroup analyses, we will include a binary covariate indicating subgroup membership in each of the regression frameworks described. We will also fit models with interactions between each subgroup and treatment group. Descriptive statistics (mean, standard deviation, counts, and percentages) and plots will be produced for all demographic, safety, and outcome variables. All analyses will be conducted using the latest version of R (R Foundation for Statistical Computing, Vienna, Austria. <http://www.R-project.org/>).

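### Prolonged ileus is too rare for the planned subgroup-interaction logistic models: at the design effect the interaction odds ratio is infinite or zero in about half of trials or more

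*Combined protocol and SAP*

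**What the plan says.** Section 9.6 first compares the proportion with prolonged ileus between arms by a Pearson chi-square test. It then adds a model: "A logistic regression model will be used to assess the association between prolonged ileus and treatment, controlling for potential confounders". The covariates of that model are neither named nor limited in number; age and gender are given as examples only for the Cox model.

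Section 9.7, headed as exploratory, states that "we will include a binary covariate indicating subgroup membership in each of the regression frameworks described", and continues: "We will also fit models with interactions between each subgroup and treatment group". Section 2.2 lists four binary subgroups: "0 vs. 1 or greater anastomoses, 0 vs. 1 or greater visceral resection", narcotic use above or below the median, and epidural or none. Section 2.3 says that primary and secondary endpoints will be measured in each subgroup, so prolonged ileus is covered.

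The endpoint is defined in Section 6.1.1: "Participants without flatus or BM for more than seven days after surgery, are considered to have a prolonged ileus". Section 1.1 gives the local background rate for first flatus or bowel movement: "in 13% of patients it takes longer than 7 days".

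The plan gives no expected event count for this endpoint, no penalised or exact method for the model, and no rule for empty cells.

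**The concern.** A logistic model is limited by its number of events, not its number of patients. The trial is sized on GI-2, an event that nearly every patient is expected to reach. Prolonged ileus is the opposite: a minority outcome that becomes rarer if the drug works.

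A treatment-by-subgroup interaction divides those few events among four cells. If one cell has no event, the maximum-likelihood interaction odds ratio runs to infinity or zero, and its standard error means nothing. This is the first-listed secondary endpoint. Without a stated rule, the analyst would have to decide what to report after seeing the data.

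**Working it through.** **Inputs from the protocol.** Control rate 13% (Section 1.1). 1:1 allocation (Section 9.1). 122 evaluable patients, so 61 per arm, and 128 enrolled, so 64 per arm (Section 9.2). Design effect: "HR = 1.59, which approximately corresponds to an improvement" (Section 9.2, for GI-2). Pooled 12 mg hazard ratios of 1.74 for bowel movement and 1.34 for time to discharge order (Section 1.2), used here as a range.

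**Assumptions.** The hazard ratio (HR) acts proportionally on time to first flatus or bowel movement. Subgroup shares are not given, except that the narcotic split is at the median and so about 50/50.

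**The plan's own figure first.** Section 9.2 claims "80% power at the one sided 0.05 significance level" with 122 patients. Freedman's formula gives [(1.59 + 1)/(1.59 − 1)]² × (1.645 + 0.842)² ≈ 119.1, so 120 events. This agrees with 122 to within 2 if every evaluable patient has the GI-2 event.

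**Expected prolonged-ileus events.** The alvimopan rate is 0.13^HR. At HR 1.59 it is 0.13^1.59 = 0.039.
- Control: 61 × 0.13 = 7.9
- Alvimopan: 61 × 0.039 = 2.4
- Total: 10.3 (10.8 at 64 per arm). The 95% range of the total is 5 to 17.

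**Main treatment odds ratio.** It is infinite or zero when the alvimopan arm has no event: (1 − 0.039)^61 = 8.8%. Simulation (4,000 trials per scenario, covariates unrelated to outcome) gave 10% with age and sex and 11% with six covariates. When the estimate is finite, the median ratio of upper to lower 95% limit is about 23 to 26. At the expected counts the odds ratio is 0.27 (95% CI 0.06 to 1.21).

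**Interaction odds ratio.** For a subgroup with share s, the cell sizes in each arm are 61s and 61(1 − s). The chance of at least one empty cell is 1 minus the product over the four cells of [1 − (1 − p)^m], where p is the arm's event rate and m the cell size. For a 50/50 split at HR 1.59, an alvimopan cell of 30.5 is empty with probability 0.961^30.5 ≈ 0.30 and a control cell with probability 0.87^30.5 ≈ 0.014. Then 1 − (0.703² × 0.986²) ≈ 0.52.

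| Assumed HR | Expected events | 50/50 | 30/70 | 20/80 |
|---|---|---|---|---|
| 1.00 | 15.9 | 6% | 15% | 33% |
| 1.34 | 11.9 | 26% | 39% | 56% |
| 1.59 | 10.3 | 52% | 61% | 73% |
| 1.74 | 9.7 | 66% | 73% | 81% |

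Rounding cells to whole patients moves these by at most about 1 point. At HR 1.59 and 64 per arm, the 50/50 figure is 49%. If all four subgroups were even and independent, at least one interaction would fail in about 79% of trials at HR 1.59 and 19% with no effect.

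A finite interaction estimate is little use either: the median ratio of upper to lower limit is about 350 at HR 1.59 and about 96 with no effect.

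**The case against.** Several stronger readings are tempting, and the documents do not support them.

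- **That the main treatment odds ratio will often be infinite.** It fails in roughly 1 trial in 10 at the design effect, about 2% at HR 1.34, and almost never with no effect. The high failure rates belong to the exploratory interactions.
- **That the treatment odds ratio will be badly biased.** In the unadjusted two-arm case at 13% and 3.9%, the geometric mean of the finite odds ratios is 0.275 against a true 0.272. Imprecision is shown; bias is not.
- **That one overloaded model is planned.** No section commits to treatment, age, sex, subgroup and interaction together. Section 9.7 reads naturally as a separate model for each subgroup. The gap in Section 9.6 is that the covariates are not named.
- **That about 10 events is a fixed figure.** It applies a GI-2 hazard ratio to a different event, for which the documents give none.
- **That the Pearson test should give way to an exact test.** The total falls below 10 in about 41% of trials at the design effect, which puts the expected events per arm below the usual guide of 5. Even so, enumeration with 61 per arm gives Pearson a two-sided size of about 4.8% to 5.1%. Fisher's test has a size of about 2% to 2.6%, and its power for 13% against 3.9% is about 30%, compared with 45% for Pearson.

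It is also fair to say that the endpoint does not depend on the logistic model. The chi-square comparison comes first, and Section 9.7 promises counts and percentages, so 0/61 against 8/61 would be readable without any model. This limits the harm. It does not rescue the interaction models, which the plan commits to fitting without saying what happens when they fail.

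**Conclusion.** The point holds for the interaction models. At the design effect, a subgroup-interaction odds ratio for prolonged ileus is infinite or zero in about 52% of trials for an even subgroup and 73% for a 20/80 subgroup. With no effect the figures are 6% and 33%. So the problem is greatest when the drug works. Section 4.4 lists epidural analgesia in the standard pathway, so the no-epidural group may be small, which would raise the risk for that subgroup.

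For the main adjusted model the conclusion is milder: an infinite or zero odds ratio in about 9% to 11% of trials, and otherwise a very wide interval.

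These figures rest on the 13% rate holding in the control arm, on the assumed hazard ratio for flatus or bowel movement, and on assumed subgroup shares. If the endpoint were read as lacking either flatus or bowel movement, the rate would exceed 13% by an amount the documents do not give. The endpoint is secondary and the interactions exploratory; the log-rank analysis of GI-2 and the sample size are untouched.

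**What to change.** - **Section 9.6, comparison.** Keep the Pearson chi-square test. Add the risk difference with a Miettinen-Nurminen score interval, which stays defined when an arm has no event.
- **Section 9.6, model.** Fit the adjusted logistic model by Firth penalised likelihood, which gives a finite estimate with empty cells. Name a small covariate set in advance. The documents do not yield an exact cap, but about 10 to 16 events argue for very few.
- **Section 9.7.** Exclude prolonged ileus from the interaction models and report event counts by subgroup and arm. Keep interaction tests for the time-to-event endpoints, where most patients contribute an event.

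The cost is a few lines of analysis-plan wording and standard R functions. The one loss is a model-based interaction estimate for this endpoint, which the expected data could not support.

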### **1.1 Disease Background**

The peritoneum is a common site of metastasis, with approximately 55,000 new cases of peritoneal metastases occurring annually in the US. Tumors that commonly metastasize to the peritoneum include gastrointestinal (colorectal, small intestine, appendix, gastric, pancreatic, gallbladder, liver), gynecologic (ovarian), and primary peritoneal (peritoneal mesothelioma, primary peritoneal serous carcinoma) malignancies. Tumor histology and extent of disease are the primary determinants of long-term outcome, but patients with peritoneal metastases typically have a poor prognosis – 16 months median survival from colorectal cancer. Treatment options for peritoneal metastases are limited as systemic chemotherapy has poor penetration of the peritoneum and many peritoneal tumors are hypovascular and can be surrounded by a viscous layer of mucin. The fact that the peritoneal cavity may represent the only site of metastatic disease in selected patients has prompted the utilization of aggressive surgical resection (cytoreduction) and hyperthermic intraperitoneal chemotherapy (HIPEC) in the treatment of peritoneal metastases. HIPEC is a method of delivering high doses of cytotoxic chemotherapy directly to the peritoneal cavity with limited systemic toxicity, and is typically performed concurrently with surgical resection of visible intraperitoneal disease (cytoreductive surgery, CRS). The combined procedure (CRS/HIPEC) generally is performed through a large midline incision and includes extensive lysis of adhesions, resection of all visible peritoneal metastases, often with multivisceral resections including bowel resections and possibly multiple anastomoses, and requires a mean of eight hours of operative time. Large case series have estimated CRS/HIPEC doubles the median survival versus systemic chemotherapy alone in certain settings (colorectal cancer, appendiceal cancer and peritoneal mesothelioma). Perioperative complications of this extensive surgery are considerable, with a 1-2% risk of mortality and 16% risk of severe morbidity. This procedure remains highly specialized and is mostly performed in a limited number of high-volume centers in the US, which include UCSD. Approximately 60-70 CRS/HIPEC procedures are performed annually at UCSD.

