LBR, large bowel resection (colectomy); SBR, small bowel resection; TAH, total abdominal hysterectomy; Alv., alvimopan; GI-3, solid food + BM/flatus; GI-2, solid food + BM; RR, relative risk; BM, bowel movement; D/C, discharge; HR, hazard ratio; RC, radical cystectomy					
 Versus Placebo					
 adjusted for sex and surgical duration					

A meta-analysis incorporating the studies listed above has been completed. The pooled

analysis revealed a significant reduction in time to GI-2 bowel function (6 mg, HR = 1.5,  $p < 0.00001$ ; 12 mg, HR = 1.59,  $p < 0.00001$ ), BM (6 mg, HR = 1.54,  $p < 0.00001$ ; 12 mg, HR 1.74,  $p = 0.0002$ ), and time to discharge order written (6 mg, HR = 1.37,  $p < 0.00001$ ; 12 mg, HR = 1.34,  $p < 0.00001$ ) versus placebo.

From a pharmacokinetic standpoint, alvimopan is metabolized by the intestinal flora and is primarily excreted in the bile, secondarily in the feces, and 35% in the urine. Its half-life is 10-17 hours, although this is longer in patients with mild-moderate hepatic impairment (Child's Pugh Class A and B) and severe renal impairment. P450 drug-interactions...

Alvimopan is FDA-approved for short-term, in-hospital use in patients at risk for postoperative ileus, particularly those following bowel resection with primary anastomosis. However, due to potential increased cardiovascular risks with long-term use, distribution of the drug is restricted to short-term use (maximum 15 doses) under a Risk Evaluation and Mitigation Strategy (REMS), which includes only institutions enrolled in the ENTEREG Access Support and Education (E.A.S.E.) Program, of which UCSD is one. The current FDA-approved dose is 12 mg orally 30 minutes to 5 hours prior to surgery, followed by 12 mg orally twice daily beginning the day after surgery for up to seven days or until hospital discharge, with a maximum of 15 doses.

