## 2.3 Endpoints

### Primary Endpoint:

The time to return of upper and lower GI function (GI-2) will be measured as follows:

- Time measured in hours from the time leaving the operating room to the later of the following two events:
  - i. Time that the patient first tolerates solid food
  - ii. Time that the patient first passes a bowel movement
- If upper and lower GI function have not occurred by the time of discharge, the patient will be censored.

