### Secondary Endpoints:

1. Prolonged ileus will be measured by the proportion of patients who do not pass flatus or bowel movement greater than 7 days from the time of surgery
2. The time to return of bowel function components will be measured in hours from the time leaving the operating room until:
  - The time to first flatus
  - The time to first bowel movement
  - The time to tolerance of solid food
3. The time to hospital discharge order written will be measured in hours from the time leaving the operating room
4. Adverse events will be measured using CTCAEv3 criteria.
5. Primary and secondary endpoints will be measured in each subgroup

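### Time to discharge order is analysed by t-test and linear regression, with no rule for patients who die or withdraw before discharge and with adjustment for post-randomisation covariates

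*Combined protocol and SAP*

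**What the plan says.** Section 2.3 defines the endpoint: "The time to hospital discharge order written will be measured in hours from the time leaving the operating room". Section 6.1.2 repeats it, with the signing of the discharge order as the end point.

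Section 9.6 gives the analysis: "We will compare the time to discharge between groups with a two-sample t-test". A linear regression is to be considered, controlling for confounders "including opioid use (i.e. total morphine equivalents) +/- epidural placement, bowel resection, and other complications". The same paragraph treats the other recovery times differently: "Log-rank test will also be used to compare the time to return of bowel function outcome", with a Cox model as an option.

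The censoring provisions concern the primary endpoint only. Section 2.3 says of GI-2: "If upper and lower GI function have not occurred by the time of discharge, the patient will be censored". Section 9.8 mentions censoring for loss to follow-up, for the interim look at that endpoint. Nothing says what value a patient has for time to discharge if no discharge order is ever written.

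On missing data, Section 9.4 says: "The primary population for all efficacy analyses is the mITT population, without imputation for missing values". Multiple imputation in the mITT population is a sensitivity analysis.

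**The concern.** Time to discharge order is a time-to-event endpoint, but the chosen methods have no place for a patient without the event. Someone who dies in hospital has the worst outcome on this endpoint and no discharge time. If that patient is left out, the arm with more deaths looks no worse on length of stay. If the time is imputed, the patient receives a discharge that never happened. With no rule in advance, the choice is made case by case.

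The adjusted analysis has a separate problem. Total morphine equivalents are calculated after discharge (Section 5.3.2), so they accumulate with the stay itself, and complications also follow randomisation. Either may be affected by treatment. Conditioning on them can remove part of a real effect or create a spurious one.

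The scale also differs from most of the evidence that the protocol relies on. Section 1.2 gives the pooled result for "time to discharge order written (6 mg, HR = 1.37" and, for 12 mg, HR 1.34. A difference in mean hours cannot be set directly beside those figures.

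**Working it through.** **1. The plan's own figure.** The plan states no power or sample size for time to discharge. The nearest figure is the primary log-rank calculation in Section 9.2 (HR 1.59, one-sided 0.05, 80% power, n = 122). Freedman's formula gives events = (1.645 + 0.842)² × [(1.59 + 1)/(1.59 − 1)]² = 6.18 × 19.27 ≈ 119.1, so 120, within 2 of 122. Schoenfeld's formula gives 115. Schoenfeld power with 122 events is 82%, the figure in the Study Summary. So 61 per arm and one-sided 5% are used below. Carrying that sidedness over to this secondary endpoint is an assumption, because Section 9.6 gives none for it.

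**2. How many patients lack a discharge time.** Section 1.1 describes the surgery "with a 1-2% risk of mortality and 16% risk of severe morbidity". Assume that all these deaths precede discharge.
- Expected deaths: 128 × 0.01 = 1.3; 128 × 0.02 = 2.6.
- Chance of at least one: 1 − 0.99^128 = 72%; 1 − 0.98^128 = 92%.
- Chance of three or more (binomial): 14% to 47%.

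So the gap will probably be met, but by few patients. Withdrawals before discharge add to these; the plan allows 5% drop-out overall and does not say how much of it falls before discharge.

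**3. Where those patients go.** A t-test and a linear regression use only patients with a value. With no imputation in the main analysis, the natural reading is exclusion. In the sensitivity analysis, multiple imputation would give a dead patient a discharge time.

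**4. Covariates.** Of the four named, bowel resection is intraoperative, and epidural placement can be defined at or before surgery. Total opioid use and other complications are measured after treatment has started.

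**5. Power at the discharge effect.** With Schoenfeld's formula at HR 1.34 and 122 discharges, power = Φ(ln 1.34 × √122 / 2 − 1.645) = Φ(1.616 − 1.645) = 49%. With 119 discharges (three deaths) it is 48%. The endpoint is not well powered by either method.

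The only length-of-stay figure is a median of 10 days (Section 1.1), so any comparison of tests needs an assumed shape. Simulation with 61 per arm, Weibull shape 2.4, control median 10 days before any lengthening, HR 1.34, one-sided 5%, and 16% of patients (the severe-morbidity rate, borrowed) with a lengthened stay:

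| Lengthening of 16% of stays | Log-rank | t-test | Difference (points) |
|---|---|---|---|
| none | 48% | 44% | 4 |
| 2-fold | 33% | 33% | 0 |
| 3-fold | 27% | 23% | 4 |
| 4-fold | 24% | 18% | 6 |

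Other assumed shapes, also one-sided 5%:
- Proportional hazards at HR 1.34 (Weibull shape 1 to 3, log-normal or heavy-tailed baseline): t-test 43-48%, log-rank 47-49%.
- Log-normal stays, 15% shorter on treatment, sigma 0.3, 0.4, 0.5, 0.6, 0.8: t-test 91, 69, 52, 40, 25%; log-rank 87, 66, 50, 39, 27%.
- 16% of stays 2.5 times longer, 15% shorter on treatment: t-test 48%, log-rank 53%, Wilcoxon 70%.

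The type I error of the t-test stayed between 4.3% and 5.6% in the null scenarios run for this second set of shapes.

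**The case against.** The best defence is that almost every patient will have an observed discharge time, so a difference in mean stay is a legitimate and easily understood estimand, and with 61 per arm the t-test holds its level. That stands. So does the point that only about one to three patients are affected by death, on an endpoint that was not used to size the trial.

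Several stronger readings are tempting and are not supported:
- A reader might infer that skewed stays make the t-test clearly inferior. The documents give no spread or shape. Under some log-normal shapes the t-test does slightly better, and where long stays do the damage, the log-rank test loses power too. In the 2.5-fold scenario Wilcoxon beats both, so long tails alone do not argue for log-rank.
- Simulating at HR 1.59, two-sided 5%, makes the gap look larger (31% against 21% with 4-fold stays). But 1.59 is the pooled GI-2 effect; the pooled 12 mg discharge effect is 1.34.
- A reader might suppose that deaths are counted as short stays. Nothing says so; the endpoint ends at a discharge order. Exclusion is itself an inference from the missing-data rule.
- An excess of deaths would not be hidden from the trial's report, because Section 9.9 summarises deaths and compares arms.
- Not all earlier discharge results are hazard ratios; the 2001 trial in Section 1.2 reports relative risks.

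**Conclusion.** The point holds as a minor one. The plan uses mean-based methods for one time-to-event endpoint while giving log-rank and Cox to others on the same clock, and it has no rule for death or withdrawal before discharge. About 1.3 to 2.6 deaths are expected among 128, with a 72% to 92% chance of at least one. This rests on the quoted 1-2% mortality and on deaths preceding discharge. The post-randomisation covariates are a further reason for change; their bias cannot be sized from the documents.

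Power is not a firm reason. In the Weibull scenarios with 16% prolonged stays the t-test trails by about 0 to 6 points, and other assumed shapes reverse the sign. The conclusion does not depend on it.

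**What to change.** Amend Section 9.6 before unblinding:
- Compare time to discharge order by the log-rank test and a Cox model, reporting the HR with its confidence interval and the median in each arm.
- Keep patients who die in hospital in the risk set as never discharged, for example censored at the longest follow-up, or treat death as a competing event. Censoring at the time of death would not solve the problem, because it assumes that the patient could still have gone home.
- Censor patients who withdraw at the time of withdrawal. Patients who only stop study drug and remain in follow-up (Section 5.5.2) should contribute their actual discharge time.
- Do not impute a discharge time for a patient who died.
- Restrict adjustment to baseline or intraoperative covariates, and drop total opioid use and postoperative complications.

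The data are the same and the methods are already in the plan, so the cost is SAP wording. The one loss is that the main effect is no longer a difference in mean hours; that can still be reported descriptively among patients discharged.
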